9.7.3.7 Descriptive Cost Analysis

The treatment-associated costs will be reported descriptively for the initiated IVF/ICSI stimulation cycles for each drug of interest, and overall, irrespective of drug. The costs will be presented per

cycle and per woman. Costs will be reported by category: treatment costs (drugs and other treatments), costs of miscarriage/birth, and adverse event costs. Costs will also be reported in total (sum of cost categories). The descriptive analysis will present the number of observations, mean, standard deviation, median, range, lower and upper quartiles. Missing observations will be reported. Costs will be reported in local currency and in Euros, using relevant exchange rates. Further, costs will be adjusted to the same calendar year using relevant consumer price indexes.

9.7.3.8 Meta-analysis

In addition to the results reported separately for each country, results will also be combined for a more holistic view and overall increased study precision. Because individual-level data currently cannot be shared across the borders of Denmark and Sweden, an MA approach based on aggregate data will be considered. The MA will be performed for the primary study objective only.

Prior to conducting MA, heterogeneity of the country-specific results will be assessed using:

- The estimated total heterogeneity.
- The Chi-squared test (significance level 0.1).
- I^2 statistic (0% to 40%: might not be important; 30% to 60%: may represent moderate heterogeneity; 50% to 90%: may represent substantial heterogeneity; 75% to 100%: considerable heterogeneity).

If high levels of heterogeneity are observed ($I^2 \geq 50\%$ or $P < 0.1$), the characteristics of the data source-specific results will be reviewed, and the possible sources of heterogeneity discussed. Results of the MA will be derived using both fixed and random-effects models, and the main model will be determined by the heterogeneity assessment. MA and country-specific results will be presented in forest plots. Further details will be presented in the SAP.

9.7.3.9 Sensitivity Analyses

Sensitivity analyses will be performed as outlined below for the primary study objective and, in one analysis (no. 3), for secondary objective 4 (Table 8).

Table 8. Overview of sensitivity analyses

No.	Topic	Main analysis		Sensitivity analysis	
		Method	Justification	Alteration to method	Justification
1	Time window for establishing stimulation cycle exposure to study drug	30 days before to 35 days after stimulation cycle index date	The IVF registers do not capture drug data comprehensively. To establish exposure of a stimulation cycle to a study drug, and one study drug only, data on dispensed prescriptions for gonadotropins are ascertained from the prescribed drug registers. A time window has been defined to capture all relevant dispensed prescriptions for gonadotropins in each cycle.	15 days before to 15 days after stimulation cycle index date	The time window for exposure establishment used in the main analysis has only been used in one prior study (27) to our knowledge. The effect of choosing a narrower time window will be explored for the primary objective and each associated outcome measure (LBR, CLBR, MC-CLBR). Otherwise the analysis will be repeated as described in 9.7.3.3 and 9.7.3.4.
2	Approach for estimation of MC-CLBR	The main analysis uses a conservative approach to estimating the MC-CLBR. It assumes none of the women who did not return for a subsequent cycle would have had a live birth, had they returned (20).	Discontinuation of IVF/ICSI treatment, i.e. , not returning for treatment after a failed attempt (live birth was not achieved) needs to be considered in the analysis of cumulative live birth rates assessed over multiple stimulation cycles.	Optimal approach to estimating the MC-CLBR. It is based on the observed data and assumes women who did not return for a subsequent cycle would have had the same live birth rates as those who did return (20).	The true MC-CLBR is thought to lie between the conservative and optimal estimates (39). Calculating both estimates will provide the range in which the actual value would be expected to fall. The analysis of MC-CLBR will otherwise be repeated as described in 9.7.3.3 and 9.7.3.4.
3	Minimum duration of follow-up for assessment of MC-CLBR and TTLB	The main analyses of the MC-CLBR and TTLB each uses a minimum of 1 year of follow-up and includes women who had initiated their first-ever stimulation	1 year is considered sufficient to achieve at least one live birth and a reasonable number of complete cycles for reliable estimates of the MC-CLBR in view of previous studies considering up to 9 (20) and 8 (21) stimulation cycles for the estimation of cumulative live birth rates with at least 1.5 and 2 years of follow-up, respectively.	Minimum follow-up period extended to 2 years, thus restricting the analysis to women who had initiated their first-ever stimulation cycle on or before 31 December 2018.	The effect of extending the minimum follow-up period on the conservative and optimal estimates of the MC-CLBR and on TTLB will be explored. The analysis of each outcome will otherwise be repeated as described in 9.7.3.3 and 9.7.3.4.

No.	Topic	Main analysis		Sensitivity analysis	
		Method	Justification	Alteration to method	Justification
		cycle on or before 31 December 2019.			
4	CLBR	The main analysis does not consider the possible impact of oocyte yield on CLBR.	Oocyte yield is not considered in the stratified analysis.	CLBR in the first, second and third stimulation cycle will be estimated by the number of oocytes retrieved in the first cycle (cycle rank expressed as observed in the study period).	Oocyte yield is known to be positively associated with CLBR (20,40,41). The effect of oocyte yield in the first cycle will be explored for the CLBR. Otherwise the analysis will be repeated as described in 9.7.3.3 and 9.7.3.4, although rates will only be reported for the IPTW-weighted cohorts.
5	Linkage between stimulation and FET cycles for the estimation of CLBR and MC-CLBR (Denmark only)	FET cycles preceded by multiple stimulation cycles, of which more than one resulted in cryopreserved embryos, are handled as follows: - If all preceding stimulation cycles used the same gonadotropin, it is assumed that the FET cycle is linked to the most recent stimulation cycle - If the preceding stimulation cycles used different gonadotropins, the FET cycle is	The DIVF does not record a link between an FET cycle and the stimulation cycle it originated from. Because clinics allowed for cryopreserved embryos to remain in the freezer while the woman started a new stimulation cycle, the origin of an FET cycle cannot be specified if it was preceded by multiple stimulation cycles which resulted in cryopreserved embryos.	Two alternative approaches will be taken for FET cycles preceded by multiple stimulation cycles which resulted in cryopreserved embryos: a) FET cycles preceded by stimulation cycles which used the same gonadotropin will be excluded b) The study period will be restricted to 2016-2020, and it will be assumed that an FET cycle is linked to the most recent stimulation cycle.	The effect of altering the FET cycle linkage method will be explored for the CLBR and MC-CLBR in order not to introduce bias by systematically including in the analysis repeat stimulation cycles in which the same gonadotropin was used (approach a). To explore the practice in more recent years in which clinics are less prone to allow banking of frozen embryos, the CLBR and MC-CLBR will be estimated using data from 2016-2020 (approach b). Otherwise the analysis for each approach will be repeated as described in 9.7.3.3 and 9.7.3.4. As described in Section 9.2.2, the assumptions made for the main and sensitivity analyses are subject to modification if deemed inadequate.

No.	Topic	Main analysis		Sensitivity analysis	
		Method	Justification	Alteration to method	Justification
		
excluded from all analyses
 
(If an FET cycle was preceded by one stimulation cycle only or multiple stimulation cycles of which only one resulted in cryopreserved embryos, that FET cycle can be reliably linked to the appropriate stimulation cycle.)
			
6	Adjustment for laboratory test results (Denmark only)	Adjusted analyses will not consider adjustment for relevant laboratory test results.	Completeness of data from the RLRR is uncertain. It is expected that laboratory test results will be available only for a subset of the Danish study population.	An adjusted analysis will be performed among the subset of Danish stimulation cycles or women, depending on the outcome measure, with at least one record of a relevant laboratory test result (see Table 1) available before the stimulation cycle index date (per cycle analyses: LBR, CLBR) or the index date (per woman analysis: MC-CLBR). This adjusted analysis will include relevant	The effect of controlling for relevant predictors of live birth, such as anti-Müllerian hormone levels, will be explored in this analysis. The adjusted analysis of the primary objective and each associated outcome measure (LBR, CLBR, MC-CLBR) will otherwise be repeated as described in 9.7.3.4.

No.	Topic	Main analysis		Sensitivity analysis	
		Method	Justification	Alteration to method	Justification
				laboratory test results as independent variables in the appropriate regression models.	

ICSI: intracytoplasmic sperm injection; IPTW: inverse probability of treatment weighting; IVF: in vitro fertilization; MC-CLBR: multiple-cycle cumulative live birth rate; RLRR: Danish Register of Laboratory Results.

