9.7.3.3 Rates and Numbers

The results of the study outcomes in the study cohorts will be estimated by calculating the outcome measures according to their definitions (see Table 7) in both original and IPTW-weighted study cohorts.

For the analyses of LBR, a woman may contribute up to one delivery resulting in live birth. For the analyses of CLBR, a woman may contribute several deliveries resulting in live birth per each stimulation cycle. The same principle applies to the analyses of clinical and ongoing pregnancies, *i.e.*, a woman may contribute several clinical and ongoing pregnancies for the analyses of CCPR and COPR, respectively.

For the analysis of MC-CLBR, where the woman is the unit of analysis, only the first occurrence of a live birth per woman within the first five stimulation cycles using the same study drug will be considered. The MC-CLBR analysis will be performed by cycle rank, *i.e.*, analyzed as the cumulative probability of a live birth up to and including the first, second, third, fourth and fifth stimulation cycle, respectively. The MC-CLBR analysis will be restricted to women who initiated their first-ever stimulation cycle during the study period.

In the assessment of MC-CLBR, it is assumed that women who did not return during the study period for another stimulation cycle after a failed attempt (*i.e.*, who did not have a live birth), did not have any live birth. Thus, for the main analysis, the MC-CLBRs will be calculated as conservative estimates (20). Optimal estimates will be provided in a sensitivity analysis restricted to the primary objective (see Analysis 2 Section 9.7.3.9).

Rates and numbers will be expressed as the rate or number per 100 units of observations with 95% CI.

Table 7. Definitions of outcome measures

Study objective	Outcome measure	Numerator	Denominator
Primary objective	LBR	Number of deliveries with at least one live birth after fresh embryo transfer	Initiated cycles with drug of interest
	CLBR	Number of deliveries with at least one live birth after one initiated stimulation cycle, including all fresh or frozen embryo transfers linked to that cycle	Initiated cycles with drug of interest
	MC-CLBR	Number of deliveries with at least one live birth after each initiated stimulation cycle in up to five cycles, including all fresh or frozen embryo transfers linked to each of those stimulation cycles	Women who initiated 1, 2, 3, 4 or 5 cycles with drug of interest

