9.7.3.4 Adjusted Odds Ratios

For the comparison of the study cohorts, the ORs (with 95% CI), adjusted for confounding factors, will be estimated by taking into account the IPTWs and using statistical modelling, such as regression analysis or general estimating equations. To estimate the adjusted ORs, the statistical model will be weighted with IPTWs and will include as covariates any variables that were used in the PS but are still unbalanced between the study cohorts after weighting. Statistical models may also be used to additionally adjust the ORs for any other potential covariates that are assessed after the initiation of the IVF/ICSI stimulation cycle and hypothesized to be associated with the given study outcomes (see Table 1 in Section 9.3.2).

For the statistical models, the following study outcomes will be considered as binary outcomes analyzed per fresh embryo transfer: live birth (*i.e.*, a primary objective outcome), clinical pregnancy and ongoing pregnancy (*i.e.*, a subset of secondary objective 1 outcomes). For the statistical models, the following study outcomes will be considered as binary outcomes analyzed per woman: MC-CLBR (*i.e.*, a primary objective outcome) will be analyzed as a binary outcome per woman in statistical models.

For the statistical models, the following study outcomes will be considered as binary outcomes analyzed per clinical pregnancies following fresh or frozen embryo transfer: pregnancy loss (secondary objective 5) and multiple pregnancy (secondary objective 6). Cycle cancellation (secondary objective 7) and OHSS occurrence (secondary objective 8) will be analyzed as binary outcomes per initiated stimulation cycle. Implantation (secondary objective 3) will be analyzed as an ordinal categorical outcome per fresh or frozen embryo transfer.

For the statistical models, the following study outcomes are considered as counts analyzed per initiated stimulation cycle: cumulative live birth (*i.e.*, a primary objective outcome), cumulative clinical pregnancy and cumulative ongoing clinical pregnancy (*i.e.*, a subset of secondary objective 1 outcomes). Also the following study outcomes are considered as counts in statistical models and

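### Table 8 sends the optimal MC-CLBR comparison (Analyses 2 and 3) to a per-woman binary model that, as specified, cannot give the adjusted odds ratio under the optimal assumption

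*Protocol*

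**What the plan says.** Section 9.7.3.3 sets the main analysis. For MC-CLBR, "only the first occurrence of a live birth per woman within the first five stimulation cycles using the same study drug will be considered", and results are reported by cycle rank. Women who do not come back after a failed attempt are taken to be women who "did not have any live birth", so "the MC-CLBRs will be calculated as conservative estimates".

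Section 9.7.3.4 sets the between-drug comparison. MC-CLBR "will be analyzed as a binary outcome per woman in statistical models", and "the statistical model will be weighted with IPTWs". The section names no weight for discontinuation and no imputation.

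Table 8 (section 9.7.3.9), Analysis 2, replaces the conservative approach with an optimal one. "It is based on the observed data", and it "assumes women who did not return for a subsequent cycle would have had the same live birth rates as those who did return". The row ends: "The analysis of MC-CLBR will otherwise be repeated as described in 9.7.3.3 and 9.7.3.4". Analysis 3 extends the minimum follow-up to 2 years for both the conservative and the optimal estimate, and refers to the same two sections.

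Section 9.7.3.5 has a method on the cycle-rank scale: IPTW-weighted Kaplan-Meier and Cox analyses of the first live birth. It is planned for time-to-live birth (secondary objective 4). Analysis 2 does not cite it.

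**The concern.** The optimal MC-CLBR is built from rank-specific rates: one minus the product, over cycle ranks, of the failure probabilities among women who started each rank. It is not the mean of an observed 0/1 outcome per woman. A model with one binary record per woman needs a value for every woman it includes. A woman who stopped after a failed cycle has an observed 0, but under the optimal assumption her contribution is a probability carried over from women who did return. Entering the observed 0 gives the conservative analysis again.

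At stake is the adjusted odds ratio for a primary outcome measure under the alternative discontinuation assumption. Section 9.9.2 relies on the pair of estimates to address what would have happened to women who discontinued. If women on one drug return more often than women on the other, the conservative odds ratio mixes the drug effect with the difference in return. The optimal odds ratio is the one that would separate them.

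**Working it through.** The protocol gives no figure for the optimal MC-CLBR or its odds ratio, so there is nothing to reproduce. It also gives no per-cycle live birth rates or return rates. The inputs below are assumptions, varied to show the range.

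**Inputs (assumed)**
- Live birth rate among women who start rank k: h = 0.30, 0.27, 0.24, 0.21, 0.18 for k = 1 to 5.
- Probability r of returning after a failed cycle: 0.60 to 0.75, constant over ranks.

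**Formulas**
- Fraction starting rank 1: a(1) = 1. Afterwards a(k+1) = a(k) × (1 − h(k)) × r.
- Conservative (non-returner scored 0): sum over k of a(k) × h(k).
- Optimal: 1 − product over k of (1 − h(k)). The return probability drops out.
- Odds ratio for A versus B: [pA/(1 − pA)] / [pB/(1 − pB)].

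**Equal drugs, return 75% (A) versus 60% (B), up to rank 5**
- Conservative A: 0.3000 + 0.1418 + 0.0690 + 0.0344 + 0.0175 = 0.563
- Conservative B: 0.3000 + 0.1134 + 0.0442 + 0.0176 + 0.0072 = 0.482
- Odds ratio with non-returners scored 0: (0.5626/0.4374) / (0.4823/0.5177) = 1.2862/0.9316 = 1.38
- Optimal, both drugs: 1 − (0.70 × 0.73 × 0.76 × 0.79 × 0.82) = 1 − 0.2516 = 0.748, so the odds ratio is 1.00

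By rank 1 to 5, the scored-0 odds ratio is 1.00, 1.12, 1.24, 1.32 and 1.38. The optimal odds ratio is 1.00 throughout. The two agree only at rank 1, where nobody has yet had the chance not to return.

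**Other assumed scenarios, up to rank 5**

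| Live birth rates | Return A vs B | Scored 0, A vs B | OR, scored 0 | Optimal, A vs B | OR, optimal |
|---|---|---|---|---|---|
| Equal | 70% vs 65% | 53.4% vs 50.7% | 1.11 | 74.8% vs 74.8% | 1.00 |
| A 10% higher (relative) | 65% vs 65% | 54.3% vs 50.7% | 1.16 | 78.6% vs 74.8% | 1.24 |
| A 10% higher (relative) | 60% vs 75% | 51.8% vs 56.3% | 0.84 | 78.6% vs 74.8% | 1.24 |

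With equal return the two odds ratios are close. With unequal return they separate, and in the last row they point in opposite directions.

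**Check that a workable method exists**

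Two methods recover the optimal result exactly in the equal-drug scenario (74.8% in both cohorts, odds ratio 1.00): a cycle-rank life table, and a per-woman analysis of women with a live birth or a failed fifth cycle, reweighted by the inverse probability of having returned. The obstacle is therefore the model as specified and not the data.

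**The case against.** The strongest reply has five parts.

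1. **The model class is open.** Section 9.7.3.4 allows regression, estimating equations or similar, and does not exclude return-probability weights or imputation. This stands as a limit: a per-woman model extended in that way would work. The text names only IPTW, however, so the method it points to is incomplete for this purpose.

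2. **The rate is obtainable, and Table 8 speaks of a range for the true rate.** This also stands. Section 9.7.3.3 works by cycle rank, and the optimal rate in each cohort follows from those counts. A reader might infer that the optimal MC-CLBR cannot be produced at all. The documents do not support that. What is missing is the adjusted odds ratio and its interval, which Analysis 2 asks for by citing 9.7.3.4.

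3. **The word otherwise signals a change.** Analysis 2 expressly replaces the conservative handling, so scoring non-returners 0 is not its intent. That is fair, but the row changes the assumption and keeps a model that has no place for it. A reader might also infer that non-returners would be dropped, leaving an analysis of completers. No section proposes that, so it should not be attributed to the plan.

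4. **Section 9.7.3.5 already gives a weighted rank-based comparison in the same analysis set.** One minus that Kaplan-Meier curve is in effect an optimal-type rate. This softens the consequence. It is nevertheless planned for a secondary objective, its contrast is a Cox rate ratio and not an odds ratio of cumulative probabilities, and Analysis 2 does not refer to it.

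5. **This is detail for the SAP, and the cross-reference recurs almost word for word in other rows of Table 8.** The SAP may well settle it. The point here is not missing detail: the protocol cites, by section number, a model that does not fit the assumption in the same row.

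**Conclusion.** The concern holds in a limited form. For the optimal estimate in Analyses 2 and 3, the protocol refers the between-drug comparison to a per-woman binary model weighted by IPTW only. As specified, that model cannot give the adjusted odds ratio or its confidence interval under the stated assumption. The optimal rates themselves are within reach.

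The size depends on how far return differs by drug, which the protocol does not report. Under the assumed rates with no drug effect, the scored-0 odds ratio is 1.11 for return of 70% versus 65% and 1.38 for 75% versus 60%, against an optimal value of 1.00. These figures illustrate the mechanism and do not forecast the study.

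A reader might go on to infer that the main analysis is wrong. It is not affected by this point: the conservative coding is stated openly, and the per-woman binary model fits it. The matter is worth correcting because it concerns a sensitivity analysis of a primary outcome measure and the repair is small.

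**What to change.** In Table 8, for the optimal estimate in Analyses 2 and 3, replace the reference to the per-woman binary model in 9.7.3.4 with an IPTW-weighted cycle-rank estimate. Either of two would do:
- one minus Kaplan-Meier on the rank scale already used in 9.7.3.5; or
- a discrete-time logistic model by rank with drug-by-rank terms.

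From it, derive the cumulative probability per cohort up to each rank, then form the odds ratio and the difference, with a bootstrap interval that resamples women. Keep the reference to 9.7.3.4 for the conservative estimate.

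The cost is a change of wording in two rows, one extra model and the bootstrap. No new data are needed.

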Randomized clinical trials (RCTs) comparing rhFSH-alfa reference product and hMG on relevant outcomes for patients and physicians are scarce with different results pointing in different directions. A small number of RCTs found no difference in implantation (8,9), pregnancy outcomes (ongoing pregnancy, clinical pregnancy and live birth) (8–10) and pregnancy loss rates per started cycle (8,9). Others have showed that, although the pregnancy outcomes did not differ between the two types of treatment, treatments with rhFSH-alfa reference product led to a significantly higher number of recovered oocytes compared to treatments with hMG (mean (\pm standard deviation [SD]): 12.29 (\pm 7.80) vs. 9.67 (\pm 5.92); $p < 0.001$) (11), (mean (\pm SD): 14.4 (\pm 8.1) vs. 11.3 (\pm 6.0); $p = 0.001$) (8) and (mean (\pm SD): 11.8 (\pm 5.7) vs. 10.0 (\pm 5.4); $p < 0.001$) (9) in fresh embryo transfer cycles.

Recently, a non-interventional study (NIS) using real world data (RWD) from 71 in vitro fertilization (IVF) centers in Germany assessed the effectiveness of the two main brands in Germany, rhFSH-alfa reference product ($n = 17,725$ women) vs. Menogon HP, an hMG product ($n = 10,916$ women), over a total of 38,234 cycles (12). In the analysis per patient, data showed better effectiveness outcomes for patients treated with rhFSH-alfa reference product than for patients treated with Menogon HP, both overall and in the GnRH agonist sub-group (the most frequently used protocol in the study period, 2007-2012) after stratification on the GnRH protocol,

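### Sensitivity analysis 4 compares the drugs on CLBR at a given first-cycle oocyte yield, which is itself a result of treatment, so in the HP-hMG comparison its cycle-1 odds ratio is not a robustness check

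*Protocol*

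**What the plan says.** In Table 8 (Section 9.7.3.9), the altered method for Analysis 4 is that "CLBR in the first, second and third stimulation cycle will be estimated by the number of oocytes retrieved in the first cycle", with cycle rank counted within the study period. The reason given is that "Oocyte yield is known to be positively associated with CLBR". The row ends: "Otherwise the analysis will be repeated as described in 9.7.3.3 and 9.7.3.4, although rates will only be reported for the IPTW-weighted cohorts". Section 9.7.3.4 is the drug-versus-drug contrast: "For the comparison of the study cohorts, the ORs (with 95% CI), adjusted for confounding factors, will be estimated by taking into account the IPTWs". Rates and between-drug odds ratios by oocyte number are therefore both planned.

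Section 9.7.3.9 attaches the Table 8 analyses to the primary objective. The Abstract says that sensitivity analyses examine how robust the main primary results are.

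Elsewhere the protocol treats oocyte number as a result of treatment. Section 8.2 makes it a secondary outcome compared between drugs (objective 2). Section 7 reports trials in which "treatments with rhFSH-alfa reference product led to a significantly higher number of recovered oocytes compared to treatments with hMG", and the same sentence says "although the pregnancy outcomes did not differ between the two types of treatment". By contrast, the stratified analysis in Section 9.7.3.6 uses age and GnRH protocol, which it describes as baseline characteristics. Neither Table 8 nor Section 9.9 warns that yield comes after the drug.

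**The concern.** In cycle 1 the drug comes first and the oocyte count follows. Suppose the reference product raises the count. Women with a given count on the reference product would then, on average, have lower ovarian reserve than women with the same count on hMG. If reserve also affects live birth, the comparison at equal count is tilted against the reference product. Separately, if extra oocytes are how a drug produces extra births, fixing the count removes that benefit. Either way the null tested is no difference at equal yield, not no difference in CLBR per initiated cycle.

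Weighting does not repair this. Section 9.7.3.1 re-estimates the propensity score within subgroups, but that balances measured baseline covariates only. Section 9.9.4 concedes that antral follicle count and AMH are unavailable in Sweden and probably available only for part of the Danish population. Even with reserve fully measured, the path from drug through yield to birth would still be blocked.

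The risk is that someone reading Table 8 as a set of robustness checks doubts a sound main result, or sees a real benefit apparently vanish.

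**Working it through.** The protocol gives no figure for Analysis 4, so there is none to reproduce. The check has an algebraic part and a numerical part.

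**Inputs from the protocol.** Section 7 gives mean (SD) oocytes, reference product vs hMG:
- 12.29 (7.80) vs 9.67 (5.92): difference 2.62
- 14.4 (8.1) vs 11.3 (6.0): difference 3.1
- 11.8 (5.7) vs 10.0 (5.4): difference 1.8

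Table 8 states a positive yield-CLBR association but gives no slope. The slope, the correlation of reserve with yield, the baseline CLBR and the oocyte bands below are therefore assumptions.

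**Algebra.** Let m1(y) and m0(y) be CLBR at yield y under the reference product and hMG, and p1(y) and p0(y) the yield distributions. If overall CLBR is equal, Σ m1·p1 = Σ m0·p0. Subtracting Σ m0·p1 from both sides gives

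Σ (m1 - m0)·p1 = -Σ m0·(p1 - p0).

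If m0 rises with yield and p1 lies higher than p0, the right-hand side is negative. Equal overall CLBR then forces lower yield-specific CLBR for the reference product, averaged over its own yield distribution. If m0 were linear, the average artefact would be the slope times the shift: each percentage point of CLBR per oocyte gives -1.8, -2.6 or -3.1 points for the three trials.

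**Simulation under a true null.** There were 2,000,000 women per arm. Yield was a rounded gamma variable with each trial's means and SDs. Live birth depended on latent reserve R only: logit = -0.85 + b·R, with b = 0.3, 0.6 or 0.9. The correlation of reserve with yield was 0.5, 0.8 or 1.0, and the bands were 0-3, 4-9, 10-15 and 16+ oocytes. Without conditioning on yield, CLBR was the same in both arms: 30.3%, 31.3% and 32.6% for the three values of b.

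Middle case (correlation 0.8, b = 0.6, overall 31.3% in both arms), reference vs hMG:

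| Trial means | 0-3 | 4-9 | 10-15 | 16+ |
|---|---|---|---|---|
| 12.29 / 9.67 | 15.6 vs 16.7 (OR 0.92) | 24.1 vs 26.5 (0.88) | 32.5 vs 36.4 (0.84) | 43.5 vs 47.5 (0.85) |
| 14.4 / 11.3 | 13.4 vs 14.3 (0.93) | 21.6 vs 23.8 (0.88) | 29.7 vs 33.7 (0.83) | 41.4 vs 45.4 (0.85) |
| 11.8 / 10.0 | 13.0 vs 15.3 (0.83) | 22.7 vs 25.4 (0.86) | 32.8 vs 36.0 (0.87) | 44.9 vs 47.6 (0.90) |

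Here the spurious difference is -0.9 to -4.0 points. Over all assumptions it is -0.4 to -7.8 points (OR 0.69 to 0.98), always against the reference product. With no yield shift it is 0.0 in every band to within 0.1 point.

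**Reverse case: the drug acts only through yield.** Overall CLBR is 35.9 vs 30.3, 40.4 vs 33.7 and 34.7 vs 30.9, real gains of 5.6, 6.7 and 3.8 points. At exactly 10 oocytes the difference is 0.0. In the three closed bands it is -0.1 to +0.5. Only the open 16+ band keeps some of it (+4.1, +4.8 and +0.7).

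**How often this would reach significance.** Cohort sizes use Section 9.5: 0.75 × 19,000 = 14,250 and 0.75 × 12,000 = 9,000 (Danish HP-hMG comparison). Under a true null with baseline CLBR 30%, oocyte SD 5.5 and reserve adding 0.03, 0.05 or 0.08 log-odds per oocyte:

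| | Shift +1.8 | Shift +1.0 |
|---|---|---|
| One pooled OR adjusted for 8 bands | 37%, 83%, 100% | 19%, 39%, 77% |
| A single band's OR, average | about 11%, 18%, 38% | 6%, 7%, 16% |

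At +1.8 the pooled ORs are 0.95, 0.92 and 0.87. Without conditioning, rejection is 4-6%. The single-band figures come from a repeat with mean yield set at 10 and reserve fixing yield completely apart from the shift. That repeat gave 37%, 81% and 100% for the pooled OR at +1.8.

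**Cycles 2 and 3.** First-cycle yield precedes the choice of drug for these cycles, so for that choice it is a pre-treatment variable. It is still a result of the first-cycle drug. Among women who stay on one drug, stratifying on it brings back the cycle-1 problem.

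**The case against.** The strongest reply is that the row asks a legitimate question. Its declared aim is to explore how yield relates to CLBR, no decision rule rests on it, and details are left to the SAP. That stands as far as the aim goes. However, the text does commit to repeating the Section 9.7.3.4 odds ratios. A between-drug odds ratio at fixed yield does not measure the yield-CLBR association, and it sits among analyses described as tests of robustness.

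Four stronger inferences are tempting, and the documents do not support them:
- **That both comparisons are affected.** The artefact needs a yield difference. Section 7 documents one for hMG only. For biosimilars it cites trials powered for non-inferiority on oocyte number and states no difference.
- **That a false significant result is near certain.** The high rejection rates belong to one pooled odds ratio adjusted for bands, a model the protocol does not specify, and they depend on assumed slopes. Single-band rates are much lower and, at the weaker settings, close to 5%. The cohort sizes count women who ever used each drug, and a woman can be in both cohorts (Section 9.2.2), so they are upper limits for first cycles.
- **That CLBR is known to be equal.** The equal outcomes in Section 7 are pregnancy outcomes in trials with fresh transfers, not CLBR.
- **That the primary result is compromised.** The main LBR, CLBR and MC-CLBR analyses do not condition on yield.

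Two modelling points also stand. The protocol gives no oocyte cut-points, so bands are a reading of its wording. Section 9.7.3.4 treats cumulative live birth as a count, whereas the simulations use a binary outcome. The algebra depends on neither.

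**Conclusion.** The point holds for the cycle-1, between-drug odds ratios of Analysis 4 in the HP-hMG comparison. They do not estimate the drug's effect on CLBR and should not count as evidence on the robustness of the primary result. They can show a deficit for the reference product when CLBR is equal, or remove a benefit that works through yield.

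The direction follows from two statements in the protocol: yield is higher with the reference product than with hMG, and CLBR rises with yield. The size does not. Under a true null it is about -0.4 to -7.8 percentage points (OR 0.69 to 0.98) over the assumed slopes, correlations and bands. For scale, Section 9.5 gives a minimum detectable difference of 1.5 points for this comparison, but that figure is for MC-CLBR in the whole cohort. For biosimilars the issue is conditional on a yield difference that the protocol does not document. This is a fault in one sensitivity analysis, and it is worth correcting because the change is cheap.

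**What to change.** Amend Analysis 4 in Table 8 as follows.

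- **Cycle 1:** remove the between-drug odds ratios by oocyte yield from the sensitivity set. Report CLBR by yield only as the yield-CLBR association within each cohort, or as a labelled exploratory mediation analysis. Placing the two cohorts' rates side by side shows the same contrast without an odds ratio. The row should therefore state that differences between drugs at a given yield are not total effects and are not evidence on robustness.
- **Cycles 2 and 3:** enter first-cycle yield as a pre-treatment covariate in that cycle's propensity score, together with the drug used in the earlier cycle or cycles, rather than as a stratum. Table 1 already lists history of stimulation with a study drug as a candidate. The variable needs to identify which drug it was.

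The cost is a wording change and somewhat less modelling for cycle 1. The downside is that there will be no drug odds ratio within oocyte strata for cycle 1.
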